#### 2.2 Secondary

- 2.2.1 To evaluate the tolerability at 8 weeks of 150mg and 250mg armodafinil in this patient population**
- 2.2.2 To assess the effect of armodafinil at 8 weeks on cognitive function in patients with high grade glioma.**
- 2.2.3 To assess the impact of armodafinil on global quality of life and other fatigue endpoints in this patient population with high grade glioma.**
- 2.2.4 Explore the correlation between the BFI, PROMIS, and PRO-CTCAE measures, as well as, the relationship of fatigue and cognitive difficulties.**

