## 16.0 STATISTICAL CONSIDERATIONS AND METHODOLOGY

### 16.1 Study Design

This is a three-arm randomized clinical trial. The primary goal of this study is to compare the response rate of patients randomized to one of two doses of armodafinil or placebo in terms of a clinically meaningful improvement in patient-reported fatigue of at least a two-point improvement in the 0-10 point Brief Fatigue Inventory usual fatigue item at eight weeks post-treatment initiation. Endpoints will be assessed per arm and compared across arms by comparing each armodafinil arm versus the placebo arm in turn. We make no adjustment for multiple comparisons as we want to err on the side of moving forward the appropriate dose into phase III testing upon the basis of promising information in the proposed trial.

The three arm randomized trial will accrue a maximum of 330 patients to randomize a 100 evaluable patients per arm based on a binary endpoint to armodafinil or placebo.

Bayesian adaptive “shadow” design: Bayes clinical trial designs are becomingly increasingly more popular as alternatives to classic Fisherian designs, especially in the phase I context (110). They have not, however, been applied to cancer control cooperative group clinical trials. As a feasibility exercise, we will use the results of this trial to “shadow” what would have happened if the Bayes design would have been used. This will provide us insights into the relative utility of the Bayes design within the context of cooperative group cancer control clinical trials. The potential advantage of the Bayes approach is that the study likelihood of efficacy is constantly monitored allowing for the possibility of early study completion and therefore a smaller number of patients put at risk (see MD Anderson Cancer Center Technical Report UTMDABTR-002-06 (98). There are a number of logistical and statistical issues that were raised in the review of the concept (which initially proposed a Bayes design) that we decided it would be more prudent to use a classic Fisherian design to run the trial and use a shadow design to obtain preliminary data for planning future cancer control clinical trials using a Bayes approach. The details for the Bayes design are attached as Appendix X.

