### 16.2 Sample Size

On average, we recruit six patients per month for GBM treatment trials. For symptom control studies with heterogeneous populations, such as N05C7 (Concerta), we were able to average 25 patients a month. We have found that symptom management trials targeting symptoms with a high prevalence have rapid accrual. Therefore, for this study, a reasonable conservative estimate for this more homogeneous population would be 8 patients a month. With 330 patients, accrual would be completed in 41 months.

The randomized design to be utilized is described below. Based on our previous work, we estimate that the response rate for the placebo arm will be 10%. We design the study with 100 patients per arm so that the Fisher’s exact test will have 80% power to detect a response rate of 25% with a two-tailed alternative and a 5% Type I error rate for each treatment comparison to the placebo. Again, we are not using a conservative multiple contrasts approach because we want to err on the side of accepting a modest armodafinil effect. We plan to accrue an additional 30 patients to account for patient cancellations, ineligibility, or major treatment violations. Therefore, there will be a maximum of 330 patients accrued to this study unless undue adverse events are encountered.

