## 16.4 Secondary Endpoints

**16.4.1 Other time points:** The same analyses carried out using the 8 week assessment data will be used for analysis of data from the other time point assessments.

**16.4.2 Other fatigue measures:** The other fatigue items ("usual", "usual" and "now") as well as the impact of fatigue items from the BFI, the PRO-CTCAE, and the summated score from the PROMIS fatigue measure will be analyzed separately in turn comparing the average of these variables for each treatment using Kruskal-Wallis testing for change from baseline to four weeks, AUC over the entire treatment period, and repeated measures ANOVA using all treatments and all time points.

**16.4.3 Cognitive function:** The same analyses outlined for the other fatigue measures will be carried out for each of the cognitive function tests.

**16.4.4 Quality of life:** The same analytical approaches will be used to compare the three treatments in terms of QOL as was outlined for the other fatigue measures.

**16.4.5 Safety and tolerability of armodafinil:** Comparison of the proportion of patients reporting adverse events via the CTCAE items will be compared across treatment arms using a Fisher's exact test.

**16.4.6 Area under the curve (AUC) and summary statistics:** For the continuous measures mentioned above, AUC summary statistics will be generated for each patient to represent the overall experience reported by patients for each endpoint (e.g. fatigue) by combining the data from baseline, weeks 4, and 8 assessment points. The average of these AUC variables will be compared between the two treatment arms using two-sample t-tests. Further summary statistics will be constructed for the categorical variables to indicate whether the patient ever responded over the entire treatment period. These categorical variables will be compared between treatment groups via Fisher's exact tests.

**16.4.7 Repeated measures analysis:** The overall experimental layout will be examined via the construction of a repeated measures model using data from all assessment time points involving the continuous variables described above. Tests for time by treatment interaction will be carried out by the profile analysis methods of Srivastava. Covariates such as age, gender and other clinical variables may be included to test their impact on the initial efficacy tests of the primary and secondary analyses described above. Use of the Optune® device will also be included as a descriptive factor.

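### The planned between-arm tolerability analysis is a Fisher test of difference with no effect estimate or interval, so a non-significant result would not establish tolerability of either dose

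*Combined protocol and SAP*

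**What the plan says.** Section 2.2.1 sets the secondary goal: "To evaluate the tolerability at 8 weeks of 150mg and 250mg armodafinil in this patient population". It gives no criterion for tolerable.

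The analysis for that goal is one sentence in 16.4.5: "Comparison of the proportion of patients reporting adverse events via the CTCAE items will be compared across treatment arms using a Fisher's exact test". It states no estimate of the difference, confidence interval, margin, significance level or sidedness. It also does not say whether the comparison is each dose against placebo or one test over three arms.

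Sample size is set in 16.2 for fatigue response alone. "We design the study with 100 patients per arm" is the stated size, and the test is specified "with a two-tailed alternative and a 5% Type I error rate for each treatment comparison to the placebo". Section 16.2 adds that "there will be a maximum of 330 patients accrued to this study unless undue adverse events are encountered".

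Three other parts of the protocol deal with safety:

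- Section 16.6 suspends accrual when related grade 4 or higher non-hematologic events reach a threshold and the rate is higher on either dose than on placebo.
- Section 16.7 sends adverse event reports to the DSMB every six months.
- Section 8.0 stops study drug in a patient with related toxicity of grade 3 or worse.

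Section 10.2 determines which events reach the routine forms: grade 2 if at least possibly related, and grade 3 to 5 whatever the attribution. Section 10.6 lists headache alone for grading at baseline and at each evaluation.

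**The concern.** The goal asks about tolerability, and the planned tool answers a different question. Fisher's test asks whether the data are compatible with equal event rates. If it is significant, harm has been shown. If it is not, the rates may be equal, or the trial may have been too small to tell. The p-value does not separate the two.

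At this sample size the second explanation is a serious one. The trial was sized for a 15-point difference in fatigue response, and a 10-point excess of an adverse event is harder to detect. Section 15.1.7 marks several reactions as dose related (headache, nausea, insomnia, depression, rash, dry mouth), so an excess on one or both doses is plausible.

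What is at stake is the information that the trial passes on. Two doses are being compared with a view to phase III, and the next team will need to know how much excess harm the data leave open for each. As written, 16.4.5 does not provide that.

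**Working it through.** **Inputs.** From 16.2: 100 evaluable patients per arm; maximum accrual 330, which is 330 / 3 = 110 per arm as an upper bound for a safety set; two-sided 5% per comparison with placebo. That level is stated for the primary endpoint and is assumed here for adverse events. The event rates are also assumptions, because the protocol gives no design rates for harm. Section 15.1.7 puts headache above 10% and several reactions at 4% to 10%, so 10% rising to 20% is used as the main case.

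**Step 1: the plan's own figure.** Section 16.2 says "we estimate that the response rate for the placebo arm will be 10"%, and that Fisher's test "will have 80% power to detect a response rate of 25"%. The uncorrected normal formula is

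n = [1.96 × √(2p̄(1−p̄)) + 0.8416 × √(p₁(1−p₁) + p₂(1−p₂))]² / (p₂−p₁)².

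With p₁ = 0.10, p₂ = 0.25 and p̄ = 0.175 this is [1.96 × 0.5374 + 0.8416 × 0.5268]² / 0.0225 = 2.240 / 0.0225 = 99.5, so 100 per arm. The stated 80% reproduces. Full enumeration of the two-sided Fisher test gives 76.2% at 100 per arm and 80.4% at 110.

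**Step 2: power for an adverse event, each dose against placebo.** For every pair of counts (x₁, x₂) with total s, the Fisher p-value is the sum of hypergeometric probabilities C(n,x)C(n,s−x)/C(2n,s) that are no larger than the observed one. Power is the sum of Bin(x₁; n, p₁) × Bin(x₂; n, p₂) over pairs with p ≤ 0.05.

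| Placebo vs dose (assumed) | Power, 100 per arm | Power, 110 per arm |
|---|---|---|
| 10% vs 20% | 44.4% | 48.0% |
| 20% vs 30% | 31.3% | 34.6% |
| 5% vs 15% | 58.6% | 64.1% |
| 5% vs 10% | 19.0% | 21.4% |
| 1% vs 5% | 19.4% | 23.7% |

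For 80% power at 10% vs 20%, about 215 per arm would be needed (80.3%). At 100 per arm even an observed doubling, 10/100 vs 20/100, gives p = 0.073; 21/100 is needed to fall below 0.05.

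**Step 3: other readings of 16.4.5, at 100 per arm.**

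- One three-arm Fisher test (20,000 simulations), placebo/150 mg/250 mg: 10/10/20% about 52.5%; 10/20/20% about 50.7%; 10/15/20% about 39.7%.
- One-sided 5%, each dose against placebo, 10% vs 20%: 56.7%.
- Both doses at 20%: at least one of the two pairwise two-sided tests is significant in about 61% of trials.

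No reading comes near 80%.

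**Step 4: what an interval adds.** Newcombe's interval combines the Wilson limits (l, u) of each arm, with placebo as 1 and dose as 2:

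lower = d − √[(p₂−l₂)² + (u₁−p₁)²]; upper = d + √[(u₂−p₂)² + (p₁−l₁)²].

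For 10/100 vs 19/100 the Wilson limits are 5.5% to 17.4% and 12.5% to 27.8%, and d = 9.0 points.

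- Lower: 9.0 − √(6.49² + 7.44²) = 9.0 − 9.9 = −0.9.
- Upper: 9.0 + √(8.78² + 4.48²) = 9.0 + 9.9 = +18.9.

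Fisher's p is 0.107. The p-value alone reports no significant difference, while the interval shows that an excess of nearly 19 points is not excluded.

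At equal observed rates the half-width is √(4.48² + 7.44²) = 8.7 points at 10% and √(6.66² + 8.88²) = 11.1 points at 20%.

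**The case against.** Several points on the other side are sound.

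- **No rule equates a null result with tolerability.** A reader might infer that a p-value above 0.05 would be read as tolerable, or would count in favour of the higher dose. The documents do not say so. Goal 2.2.1 is to evaluate tolerability, not to demonstrate it, and the one closing rule for the 250 mg arm (16.7.1) rests on effect size.
- **Fisher's test is not the only safety provision.** The grade 4 or higher rule needs no significance test, the DSMB reviews adverse events, and 16.1 says endpoints are assessed per arm, so per-arm proportions can be expected. These are real safeguards. However, 16.6 ignores lower grades, the DSMB review has no stated criterion for them, and per-arm proportions alone give no difference or interval.
- **The miss rate depends on the reading.** It is tempting to say that a doubling from 10% to 20% is missed more than half the time. That holds pairwise at two-sided 5% (55.6% at 100 per arm, 52.0% at 110). With a three-arm test the miss rate is about 47% to 49% if one or both doses are at 20%, and about 60% for 10/15/20%. With a one-sided 5% test it is about 43%.
- **The phase III remark in 16.1 concerns multiplicity.** The text "we want to err on the side of moving forward the appropriate dose into phase III testing upon the basis of promising information" explains why the dose comparisons are not adjusted. It is not a statement about how harm will be weighed. Applied to adverse events, the absence of adjustment would make harm easier to flag.
- **Low power for harm is normal in a trial sized for efficacy.** This is true, and it is a reason to report intervals rather than rely on a p-value.
- **Not every reaction in 15.1.7 can be tabulated at all grades.** Sections 10.2 and 10.6 do not require those data, and the fix has to respect that.

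**Conclusion.** The point stands as a weakness of method, not as an error that would invalidate the trial. Section 16.4.5 is the only planned between-arm analysis for goal 2.2.1 and specifies a test of difference with no estimate or interval. For an assumed rise from 10% to 20%, power is about 44% to 48% for each dose against placebo at two-sided 5%, and about 40% to 53% for a single three-arm test at 100 per arm. A non-significant result would therefore not establish tolerability.

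The conclusion rests on assumed event rates, on a significance level borrowed from the primary endpoint, and on 100 to 110 patients per arm. Other rates change the figures (19% to 64% across the pairs in the table) but not the conclusion. It does not depend on any claim about how the trial team would interpret a null result, on which the documents are silent. A change is advisable because it is cheap and lets the trial state how large an excess it can exclude.

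**What to change.** Amend 16.4.5 as follows.

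1. For each dose against placebo, report the event proportions and the risk difference with a two-sided 95% interval (Newcombe or Miettinen-Nurminen).
2. Do this for three groups that match what the forms collect under 10.2 and 10.6: headache; grade 2 or worse events at least possibly related; and grade 3 or worse events regardless of attribution. State in the table that grade 1 events other than headache, and unrelated grade 2 events, are not required data.
3. Describe tolerability by the excess that the interval does not exclude, and state that p > 0.05 is not evidence of tolerability.
4. Keep Fisher p-values as descriptive, and say whether they are pairwise or three-arm, and at what level and sidedness.

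This gives a description, not a pass/fail rule. A yes-or-no statement would need a margin set in advance by the clinical team; none is proposed here.

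The cost is SAP wording and a few table columns on data already collected, with no added patients or visits. The downside is that intervals of about ±9 points at equal 10% rates and ±11 points at 20% will make the tolerability statement less favourable than a bare non-significant p-value. Interval and test can also disagree at the margin: 10/100 vs 20/100 gives a Newcombe interval of about 0.0 to 19.9 points, with the lower limit just above zero, while Fisher's p is 0.073. The SAP should say beforehand that the interval is the basis for the description.

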### 2.0 GOALS

#### 2.1 Primary

To determine preliminary efficacy measured by patient reported fatigue using the Brief Fatigue Inventory (BFI) at 8 weeks of two doses (150mg and 250mg) of armodafinil in treating moderate fatigue compared to placebo in patients with high grade glioma.

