**15.1.7 Known potential toxicities**

The use of armodafinil is contraindicated in patients with hypersensitivity to armodafinil, modafinil, or any component of the formulation.

Use is not recommended in patients with a history of angina, cardiac ischemia, recent history of MI, left ventricular hypertrophy, or patients with mitral valve prolapse, who have developed mitral valve prolapse syndrome with previous CNS stimulant use.

Angioedema and hypersensitivity (with rash, dysphagia, and bronchospasm) have been observed with armodafinil. Small average increases in mean systolic and diastolic blood pressure were seen in patients with narcolepsy taking armodafinil when compared to placebo.

Serious and life-threatening rashes including Stevens-Johnson syndrome, toxic epidermal necrolysis, and drug rash with eosinophilia and systemic symptoms have been reported with modafinil, the racemate of armodafinil. Most cases have been reported within the first 5 weeks of therapy.

In pre-approval narcolepsy, OSA and SWD controlled trials of armodafinil, anxiety, agitation, nervousness, irritability, and depression were reasons for treatment

discontinuation more often than for placebo. Cases of suicide ideation were also observed in clinical trials.

The use of armodafinil may impair the ability to engage in potentially hazardous activities.

The agent should be administered at a reduced dose for patients with severe hepatic impairment. There is inadequate information to determine the safety and efficacy of dosing patients with severe renal impairment. Elimination of the agent and its metabolites may be reduced in elderly patients. Consideration should be given to the use of lower doses in this population.

Headaches are dose related and reported in > 10% of patients. Adverse reactions reported in 4 to 10% of patients include nausea (dose related), dizziness, insomnia (dose related), anxiety, and diarrhea. Adverse events reported in < 4% of patients include: depression (dose related), dyspepsia, fatigue, palpitations, rash (dose related), upper abdominal pain, agitation, anorexia, constipation, contact dermatitis, decreased appetite, depressed mood, attention disturbance, dyspnea hyperhidrosis, increased heart rate, flu-like syndrome, loose stools, migraine, nervousness, pain, paresthesia, polyuria, pyrexia, thirst, tremor, xerostomia (dose related), and vomiting.

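### Section 16.4.5 tests adverse events without using dose order, although section 15.1.7 names six dose-related harms; a supplementary trend test for those six would add modest power at almost no cost

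*Combined protocol and SAP*

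**What the plan says.** Section 16.4.5 gives the whole safety analysis in one sentence: "Comparison of the proportion of patients reporting adverse events via the CTCAE items will be compared across treatment arms using a Fisher's exact test". It does not say whether this is one 3x2 test over all arms or two 2x2 tests. Section 16.1 suggests the second: "Endpoints will be assessed per arm and compared across arms by comparing each armodafinil arm versus the placebo arm in turn". The same section adds "We make no adjustment for multiple comparisons".

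The arms are ordered by dose, since the primary goal (2.1) concerns "two doses (150mg and 250mg) of armodafinil" against placebo. Section 15.1.7 states a direction for some harms: "Headaches are dose related and reported in > 10% of patients", and "Adverse reactions reported in 4 to 10% of patients include nausea (dose related), dizziness, insomnia (dose related), anxiety, and diarrhea". It also marks depression, rash and xerostomia as dose related, within the group reported in under 4% of patients. That makes six terms. Headache is the one event that section 10.6 requires to be graded at baseline and at every evaluation.

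No other section supplies a dose-trend analysis of adverse events. The logistic model in 16.4.8 concerns fatigue responders, 16.4.7 covers continuous variables, and the stopping rule in 16.6 asks only whether either active arm exceeds placebo.

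**The concern.** The protocol expects six named harms to rise with dose, then plans a test that gives the same p-value however the three arms are ordered (3x2 version) or never sets the two doses on a common scale (pairwise version). Where risk does rise at each step, a test that uses the order detects it more often from the same patients.

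Tolerability of the two doses is the first secondary goal (2.2.1), and section 16.1 says the trial should inform which dose goes to phase III. For a harm, the costlier error is a missed signal, and each lost point of power makes it likelier that a real dose-related harm is reported as showing no significant difference between arms. Section 16.4.5 also plans no effect estimate with a confidence interval, which would show how large a harm a non-significant result leaves open.

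**Working it through.** **Inputs.** From the documents: 100 patients per arm (16.2, "We design the study with 100 patients per arm"), two-sided 5% per comparison (16.2), doses 0, 150 and 250 mg (2.1), six dose-related terms (15.1.7). Assumed: all event rates by arm. Using 100 per arm for safety is also an assumption; 16.2 sets that number for the primary endpoint.

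**Check against the plan's own figure.** The plan states no power for safety. It states 80% for the primary endpoint, 10% against 25%. The pooled normal formula gives (0.15 − 1.96 × √(2 × 0.175 × 0.825 / 100)) / √((0.10 × 0.90 + 0.25 × 0.75) / 100) = 0.0447 / 0.0527 = 0.85, and Φ(0.85) = 80.2%, so the 80% reproduces. Full enumeration of Fisher's exact test gives 76.2%. That difference is a separate matter; the enumeration method is the one used below.

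**Tests.** Let x₀, x₁, x₂ be the numbers with the event and m their sum.

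- 3x2 Fisher: given m, each table has probability C(100,x₀) C(100,x₁) C(100,x₂) / C(300,m). The p-value sums the probabilities of all tables no more probable than the observed one.
- Either pair: 2x2 Fisher for 150 mg versus placebo and for 250 mg versus placebo, each at 5% unadjusted; a hit on either counts.
- Exact trend: T = 0·x₀ + 150·x₁ + 250·x₂, with null mean m × (0 + 150 + 250)/3 = 133.3m. The p-value sums the same conditional probabilities over tables with |T − 133.3m| at least as large as observed.

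Power is the sum, over all tables with p ≤ 0.05, of the product of three binomial probabilities.

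**Risk rising at each step (power, %).**

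| Assumed rates, placebo/150/250 | 3x2 Fisher | 250 mg vs placebo only | Either pair | Exact trend | Gain over 3x2 | Gain over either pair |
|---|---|---|---|---|---|---|
| 10/17/23% | 59.7 | 64.8 | 68.0 | 69.8 | 10.1 | 1.8 |
| 10/16/20% | 40.6 | 44.4 | 49.4 | 50.1 | 9.5 | 0.7 |
| 5/10/14% | 47.9 | 50.4 | 54.4 | 57.1 | 9.2 | 2.7 |
| 3/6/10% | 40.2 | 42.4 | 44.7 | 50.5 | 10.3 | 5.8 |
| 4/6/10% | 28.7 | 29.0 | 30.7 | 35.9 | 7.2 | 5.2 |
| 1/2/4% | 14.3 | 9.6 | 10.1 | 22.8 | 8.5 | 12.7 |

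The rates 4/6/10% (nausea, insomnia) and 1/2/4% (rarer terms) stay close to the incidence bands in 15.1.7. The rates 5/10/14% and 3/6/10% exceed those bands on active drug.

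**No effect (false-signal rate, %).**

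| Rate in all arms | 3x2 Fisher | One pair | Either pair | Exact trend |
|---|---|---|---|---|
| 10% | 4.6 | 2.9 | 5.3 | 4.6 |
| 5% | 4.1 | 2.1 | 3.9 | 4.4 |

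The trend test's gain is not bought with an inflated error rate.

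**Other shapes (power, %).**

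| Assumed rates | Shape | 3x2 Fisher | Either pair | Exact trend |
|---|---|---|---|---|
| 10/10/22% | harm only at 250 mg | 67.1 | 59.6 | 61.7 |
| 10/20/20% | plateau | 50.9 | 61.0 | 51.5 |
| 10/25/15% | not monotone | 72.4 | 76.9 | 20.2 |

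The scores matter slightly: at 10/15/20% the exact trend test has 49.8% with scores 0/150/250 and 47.1% with 0/1/2, so they should be fixed in advance.

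**The case against.** The strongest reply is that the plan fits its goal. Goal 2.2.1 asks about each dose; dose-versus-placebo comparisons answer that directly, while a significant trend does not say which dose is harmful. Fisher's test is valid, and arm-level proportions will be visible whatever the p-value. This stands, and it is why the trend test should supplement the planned comparison.

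Three stronger readings are tempting, and the documents do not support them.

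- **That the pairwise plan is badly conservative.** A single comparison has a true size of 2.1% to 2.9%, but 16.1 plans both comparisons without adjustment. The false-signal rate over the two is 3.9% to 5.3%, close to nominal. Setting the trend test against 250 mg versus placebo alone overstates the gain in the same way.
- **That a trend test should be the main test for every CTCAE term.** Section 15.1.7 does not call dizziness, anxiety or diarrhea dose related, and the trend test performs badly when risk is not monotone (20% against 72% for the 3x2 test at 10/25/15%).
- **That the plan would miss harms which a trend test would reliably find.** Near the incidence bands in 15.1.7 every test is weak: at 4/6/10% the trend test still misses about 64% of the time, and at 1/2/4% about 77%. Section 10.2 also requires routine reporting of grade 2 events only when at least possibly related, plus all grade 3 and above, so recorded rates may be lower still for terms other than headache.

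**Conclusion.** The point holds as a minor, optional improvement. The planned safety test ignores a dose order that the protocol itself states for six harms, and nothing elsewhere in the plan uses it. The test is valid and the plan does not contradict itself here.

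The size of the loss depends on what 16.4.5 means. Against one 3x2 test, the exact trend test gains about 7 to 10 points. Against two dose-versus-placebo tests with a hit on either counting, it gains about 1 to 6 points, rising to about 13 for very rare events (1/2/4%: 23% against 10%). These figures rest on 100 patients per arm, two-sided 5%, assumed event rates and risk that rises at each step. On a plateau, or where risk is not monotone, the advantage disappears or reverses; where harm is confined to 250 mg, the trend test falls behind the 3x2 test.

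**What to change.** In section 16.4.5:

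1. State whether Fisher's test is one 3x2 test or two dose-versus-placebo tests, and keep it for all CTCAE terms.
2. For headache, nausea, insomnia, depression, rash and xerostomia, add a prespecified exact Cochran-Armitage trend test with scores 0, 150 and 250, reported beside Fisher's test and not in its place.
3. Report the risk difference with a 95% confidence interval for each dose versus placebo.

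This needs a few sentences and a few lines of code. It needs no new data or patients and changes no dose or clinical rule. The statistical cost is one more test for six terms: if none of the six harms were related to treatment, about 6 × 0.046 ≈ 0.3 false trend signals would be expected (using the size at 10% rates), so the result should be labelled supportive. The trend test's weakness when harm is confined to 250 mg, on a plateau or with non-monotone risk is covered by keeping the Fisher comparisons.
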